1.0 Study Summary

Study Title	Scale it up: Effectiveness-implementation research to enhance HIV-related self-management among adolescents and young adults: Tailored Motivational Interviewing Implementation Intervention (TMI)
Study Design	Multi-site clinical intervention targeting health care providers
Primary Objective	Test a multi-faceted Tailored Motivational Interviewing Implementation intervention (TMI), based on the DAP to scale up an EBP in multidisciplinary adolescent HIV care settings while balancing flexibility and fidelity
Secondary Objective(s)	Sustainment through communities of practice (CoP)
Research Intervention(s)	multi-faceted Tailored Motivational Interviewing Implementation intervention
Study Population	10 Adolescent HIV sites in the US
Sample Size	Average of 15 providers per site (current N=139)
Study Duration for individual participants	3 years
Study Specific Abbreviations/ Definitions	Tailored Motivational Interviewing Implementation intervention (TMI); Dynamic Adaptation Process (DAP); implementation science (IS); youth living with HIV (YLH); Motivational Interviewing (MI); evidence-based practice (EBPs); exploration, preparation, implementation, and sustainment phases (EPIS); Communities of Practice (CoP); Implementation team (iTeam)

PROTOCOL TITLE: TMI

2.0 Objectives*

The goal of this proposal is to test a multi-faceted Tailored Motivational Interviewing Implementation intervention (TMI), based on the Dynamic Adaptation Process (DAP) to scale up an EBP in multidisciplinary adolescent HIV care settings, while balancing flexibility and fidelity.

To address this goal, we are using a dynamic wait-listed design to determine the impact of TMI on the integration of MI with fidelity in 10 adolescent HIV sites in the United States with an average of 15 providers and 100 patients each. At the start of TMI, clinics were randomly assigned in 5 blocks of (2 sites each) sites 3 months apart. Role play completion is considered consent to participate. Provider competence ratings (primary outcome) are collected quarterly during pre-implementation, implementation, and sustainment. Across sites, providers preceding the implementation intervention form a control or comparison group, and the providers following the start of the implementation intervention form the intervention group. As each block completes a year of implementation, those sites are re-randomized to internal facilitation (a person from each site will be chosen to be an MI supervisor to be available for ongoing coaching) plus Communities of Practice (CoP), or CoP only. For the CoP, the site will decide how to meet as a group to continue MI practice.

3.0 Background*

The NIH Office of AIDS Research called for implementation science (IS) to address the behavioral research-practice gap. Motivational Interviewing (MI) is the only behavioral intervention to date shown to be effective to improve self-management for youth living with HIV (YLH). MI was also the only intervention to demonstrate success across the youth HIV care cascade. MI interventions can target multiple behaviors and be delivered by multiple provider-types as is common in adolescent HIV care settings. Finally, MI is already embedded in the clinical guidelines for HIV care and HIV risk reduction.

Implementation Science is the scientific study of methods to promote the uptake of research findings and evidence-based practice (EBPs) to improve the quality of behavior change approaches in health care settings. A primary challenge of scaling up EBPs is the balance of flexibility (adaptation to context) and fidelity (provider adherence and competence). The Dynamic Adaptation Process (DAP) guides tailoring of MI implementation at the exploration, preparation, implementation, and sustainment phases (EPIS) of scale up. The goal of this project is to test a multi-faceted Tailored Motivational Interviewing Implementation intervention (TMI), based on the DAP to scale up an EBP in multidisciplinary adolescent HIV care settings while balancing flexibility and fidelity.

4.0 Study Endpoints*

One of the primary goals of this study is to help participants hone and develop new MI skills to increase medication and treatment adherence among the youth that they serve in HIV clinics. Thus, the primary outcome is improving MI skills among the health care provider participants in the study, with secondary goals of improving health outcomes for youth living with HIV and risk reduction among youth at risk for contracting HIV.

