2.2. Objectives/Research Hypotheses

2.2.1. Primary Objective

The objective of this study is to determine the effect of TMI on provider competency.

Specific Aims:

- 1) To determine the effect of TMI on provider MI competency, and secondarily HIV care cascade outcomes, in 10 multidisciplinary adolescent HIV care teams.
- 2) To compare internal facilitation plus Communities of Practice (CoPs) to CoPs alone in sustaining fidelity.
- 3) To explore the role of the barriers and facilitators to implementation identified in the EPIS model as these impact on provider MI competency.
- 4) To determine the cost effectiveness of TMI with or without internal facilitation sustainment by combining fidelity and cascade outcomes with monies spent on implementation strategies.

Primary Hypotheses:

- 1) MI competency will increase during the TMI phase relative to the baseline phase.
- 2) During the sustainment phase, the level of MI competence from the Implementation phase will be maintained. (Exploratory)
- 3) During the sustainment phase, CoP with IF will have better maintenance of MI competence relative to CoP only. (Exploratory)
- 4) Cascade-related outcomes—including viral load detectability, number of clinic visits among YLH, number of youth tested and linked to care—will improve during the implementation and sustainment phases relative to the baseline phase.

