2.3.2. Secondary Outcomes

The secondary outcome is HIV Cascade Variables.

- Record/chart abstraction will be conducted for all patients in care at the site for
 - the 12 months prior to the start of implementation;
 - the 12 months during implementation; and
 - 6 months after the end of the implementation intervention.
- These data will include the date of diagnosis and care entry, antiretroviral adherence prescriptions, CD4 counts, viral load, and the CD4 and viral load testing dates.
- Retention in care variables will include: missed visits (using an absolute count or a minimum number of missed visits); Appointment adherence (proportion of scheduled visits that are kept); Persistence/constancy (a minimum standard of visits/time period, attending at least 1 visit every 90 days); and gaps in care (no more than 4 months without a visit). In addition, number of youth receiving HIV C&T services from the site as well as number of new diagnoses identified and linked to care will also be captured.

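### Linkage to care is planned as a raw count that cannot show whether linkage improved; separately, the risk-reduction goal has no outcome

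*Protocol*

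**What the plan says.** Protocol 4.0 makes provider skill the primary outcome, "with secondary goals of improving health outcomes for youth living with HIV and risk reduction among youth at risk for contracting HIV". The prevention goal is not incidental: SAP 4.3 admits prevention as well as care providers, and protocol 16.0 expects benefit to prevention programmes.

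Hypothesis 4 in SAP 2.2.1 lists viral load detectability, clinic visits and testing and linkage, and ends: "number of youth tested and linked to care—will improve during the implementation and sustainment phases relative to the baseline phase". It stands under the primary hypotheses and, unlike Hypotheses 2 and 3, is not marked exploratory.

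For youth not already in care, SAP 2.3.2 captures the "number of youth receiving HIV C&T services from the site as well as number of new diagnoses identified and linked to care". No denominator is given. The abstraction windows are "the 12 months prior to the start of implementation", "the 12 months during implementation" and "6 months after the end of the implementation intervention".

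The outcome table in SAP 5.2.1 names only viral load for the cascade. SAP 5.4.2, for analysis of the secondary objective, is a heading with no text.

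**The concern.** A reader will take a larger number linked as better linkage. But a site can link more youth because it tested more, because more of those tested were positive, or because it linked a larger share of those diagnosed. Only the last is linkage performance. A single count cannot say which of the three changed, and two of them can outweigh the third.

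The risk is a directional statement about linkage, in either direction, that the data do not support. A second, separate gap is that a goal named in the endpoints section of the protocol has no outcome in either document, which invites readers to look for an answer in whatever was counted for at-risk youth.

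**Working it through.** The plan gives no expected count, positivity or linkage proportion, so there is no figure to reproduce. SAP 3.3 reports 1462 individuals for the cascade outcomes but does not split them by tested, diagnosed or linked.

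**Formula.** Number linked = tested × positivity × proportion linked.

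**Inputs, all assumed:** 300 tested per 12 months, positivity 2% (range 0.5% to 5%), 75% linked.

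| Scenario | Tested | Positivity | Linked share | Number linked | Change |
|---|---|---|---|---|---|
| Reference | 300 | 2.0% | 75% | 4.50 | – |
| Positivity 30% higher, nothing else | 300 | 2.6% | 75% | 5.85 | +30% |
| Positivity 30% lower, nothing else | 300 | 1.4% | 75% | 3.15 | -30% |
| Positivity 30% higher, linkage worse | 300 | 2.6% | 62% | 4.84 | +7% |
| Positivity 30% lower, linkage better | 300 | 1.4% | 90% | 3.78 | -16% |
| Testing 25% higher, positivity 20% lower | 375 | 1.6% | 75% | 4.50 | 0% |
| Testing 50% higher, positivity 20% lower | 450 | 1.6% | 75% | 5.40 | +20% |
| Nothing changed, 6-month window | 150 | 2.0% | 75% | 2.25 | -50% |

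The percentage changes do not depend on the starting level, because the formula is a product. The reference count is 300 × 0.005 × 0.75 = 1.13 at 0.5% positivity and 300 × 0.05 × 0.75 = 11.25 at 5%.

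**When the count misleads.** If linkage falls from 75% to 62%, the count still rises once diagnoses rise by more than 75/62 - 1 = 21%. If linkage rises from 75% to 90%, the count still falls once diagnoses fall by more than 1 - 75/90 = 17%. The proportion linked reads 62% and 90% in these cases, whatever the number of diagnoses.

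**Precision of the proportion.** Taking the 300 as per site, ten sites give 300 × 10 × 0.02 = 60 new diagnoses in 12 months. The 95% half-width is 1.96 × √(0.75 × 0.25/60) = 11 percentage points. At 0.5% positivity (15 diagnoses) it is 22 points, and at 5% (150 diagnoses) 7 points. For one site with 6 diagnoses it is 35 points. These figures ignore clustering by site, which could widen the pooled ones.

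**Risk reduction.** Set against protocol 4.0, SAP 2.3.2 and 5.2.1 contain no measure of risk behaviour, prevention uptake or HIV incidence. Number tested measures testing uptake, which is a different thing.

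**The case against.** A reader might infer that the SAP scores success as more infections, or that its success measure falls when prevention works. The documents do not support that.

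- **No scoring rule exists.** The SAP says only that outcomes will improve. An increase is the natural reading of a number linked, but no direction or analysis is written down. This stands.
- **Linkage is listed as a cascade outcome.** Nowhere is it put forward as the measure of risk reduction. The unmeasured goal and the missing denominator are two gaps, not one conflict. This stands.
- **The count follows infections only with testing and linkage fixed.** More testing can cancel or reverse a fall in positivity, as the table shows, and positivity also depends on who is tested. This stands, and it also shows why one number mixing three processes cannot be interpreted alone.
- **Small counts would rarely reach p < .05, the threshold in SAP 5.1.1.** Treating counts as independent Poisson over ten sites, 45 against 58.5 gives z = 13.5/√103.5 = 1.33 (p about 0.18). For 45 against 48.4, z is about 0.35, and for 45 against 37.8 about 0.79. So none of these illustrations would be declared a change. But SAP 5.1.1 reports estimates and intervals for all effects, and a non-significant count is no more informative about linkage.
- **Other cascade outcomes do not share the problem.** Viral load, appointment adherence, persistence and gaps in care are not counts of new diagnoses. This stands and limits the point to linkage.

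**Conclusion.** The point holds for linkage. As a raw number, it cannot support a conclusion that linkage improved or worsened, and under plausible combinations it moves the wrong way: +7% while linkage falls by 13 points, or -16% while it rises by 15. The identity needs no assumption; the sizes rest on assumed inputs. The unequal windows add a halving in the last period that has nothing to do with performance.

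Separately, the risk-reduction goal in protocol 4.0 has no outcome, so the trial cannot report on it.

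One uncertainty affects the remedy. The wording "number of new diagnoses identified and linked to care will also be captured" can mean one joint count or two, so the documents do not settle whether undiagnosed linkage failures (new diagnoses not linked) can be recovered. The primary outcome is untouched, so this is a correction to a secondary outcome and not a threat to the main result.

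**What to change.** - In SAP 2.2.1 and 2.3.2, define the linkage outcome as the proportion linked to care among youth newly diagnosed at the site in each window.
- Confirm that all new diagnoses, linked or not, are held as a separate count. If they are not, abstract that count.
- Report number tested and number linked as rates per site-month, because the windows are 12, 12 and 6 months.
- Report new diagnoses per youth tested descriptively, with no direction of benefit.
- Draw no conclusion on risk reduction from these data, and say so in protocol 4.0.

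**Cost.** Only wording, if diagnoses are already counted separately; otherwise one further count per site and window, 10 × 3 = 30 figures. No written analysis is displaced, since SAP 5.4.2 is empty. The downside is precision: with few new diagnoses per site, the interval for the proportion will be wide.

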5.0 Study Intervention

PROTOCOL TITLE: TMI

TMI Implementation Intervention Strategies:

Pre-Implementation: Key stakeholders were identified for the Implementation team (iTeam). The iTeam have conference calls during the baseline period to discuss barriers and facilitators and iteratively draft locally-customized implementation strategies until iTeam members and experts "approve" the strategies. The first iTeam call is initiated 6 months prior to the start of the Implementation phase at each site and monthly iTeam calls start 3 months prior to the start of the Implementation phase at each site. In addition, the iTeams have the option of implementing an anonymous consumer satisfaction of clinic environment survey, which will be provided via a Qualtrics survey link and anonymous data is shared with the study team. This survey is administered 1-month prior to the workshop, 1 month after the workshop, and 1 year after the workshop.

Implementation. Adapted training begins in this phase. The iTeam continues to meet monthly to review adherence to program requirements and external MINT facilitator reports and recommends further adaptations as necessary while maintaining fidelity to minimum requirements detailed below.

Initial Workshop. Ten hours of group workshop training were delivered by members of MINT ([name], [name], [name]), adapted from findings of sequential analysis in our pilot work and interactions with the local iTeams. MI training relies on experiential activities developed by the network while minimizing didactic presentations. Cooperative learning methods allow staff members to coach each other in small groups to promote experiential learning and group cohesion. Group MI methods are included to increase intrinsic motivation for implementation strategies. Non-TMI participants to attend the workshop if desired. Attendance was capped at 25 so that sufficient individualized attention could be given to attendees, and TMI participants were prioritized for attendance. TMI participants were only eligible to continue beyond baseline participation if they attended at least 50% of the workshop.

Fidelity Monitoring. Provider MI competency will be measured with the MI Coach Rating Scale (see Measures below) during the baseline, implementation, and sustainment periods. Individual coaching following each quarterly assessment will be triggered by a provider falling below the competency threshold on the standardized patient interaction for the quarterly assessments during the implementation period only. To define this threshold, during the project start-up phase, [name] will lead an IRT-based standard setting process. To accomplish this, there are several steps: (1) Enlist a sample of approximately 8 - 10 MI experts. (2) Obtain each expert's (independently rated) pool of "essential" MI items. This will be achieved using a survey format that is similar to traditional "bookmark" standard setting procedures, with the expert indicating whether or not each item is essential for acceptable TMI competence. (3) Compute the average "difficulty" of the selected items for each expert based on the item difficulty calibrations from the NHLBI-funded center grant, and compute the average difficulty across experts. (4) Compute confidence bounds for the mastery level using the standard error of the Rasch measure. (5) Construct the competence threshold score (i.e., the standard) as the criterion score + mastery level \pm confidence level. (6) Apply the competence standard to data from the previous projects with scale (NHLBI-funded center grant and ATN 128), and, as a source of validity evidence, test whether key outcomes differ for providers above and below the competency threshold.

PROTOCOL TITLE: TMI

Coaching Feedback. Providers receive written feedback regarding their competency scores based on the RA coding of recordings of standard patient interactions. All participants will receive two, 1-hour coaching sessions by a MINT trainer following the workshop, but before the next quarterly assessment. Participants may receive a 45-minute coaching session by a MINT trainer following each quarterly assessment during the implementation period only. This coaching is required if scores fall below competency and optional if scores are above competency. The standardized coaching includes a brief interaction to elicit change talk around MI implementation, feedback on two highest and two lowest ratings, review of the role play audio recording and interactive coaching activities (e.g., role plays) targeting the lowest ratings.

Organizational Supports. While many aspects of this implementation strategy are adaptable, organizational leadership will review data on completion of the role play and coaching sessions and will determine corrective action for suboptimal adherence. Each site will receive the same incentive budget (equivalent of \$50 per staff member) and will determine whether incentives will be provided episodically or after program completion. The iTeam will decide how to deliver incentives (i.e., directly to individuals for completion of program requirements, utilize a lottery system, or provide a group reward when all site participants adhere to program requirements); however, beginning in cycle 8, participants must be provided at least a \$10 incentive for completing role plays.

Sustainment. The iTeam will guide the site(s) to develop a community of practice (CoP). CoPs are based on a view of learning as an individual and social phenomenon rather than a one-way transfer of formal knowledge between groups or individuals. By having providers participate in the implementation phase, a CoP is already beginning to develop at the sites. The iTeam will guide the continued development of the CoP as needed by assisting with scheduling and setting meeting agendas to encourage MI practice, peer coaching and potentially fidelity monitoring, and prevent drift. In addition to CoP, half the sites will be randomized to receive 0.1 FTE of funding during the sustainment period for an internal facilitator who will be trained to continue quarterly fidelity monitoring and coaching feedback when scores fall below competency. The funding may be split among two facilitators to account for staff turnover. The iTeam will choose the facilitator(s) based on participant competency, provider interest and motivation, and the participant's role within the organization. The chosen internal facilitator will be given the option of declining this position for any reason. If they choose to accept the appointment, they will be asked to sign a release of information to help the study team and site ensure their ability to act in the role of internal facilitator. The internal facilitator will be able to choose how much information is shared and with whom the information will be shared.

6.0 Procedures Involved*

Participants will be part of a multi-phase motivational interviewing (MI) implementation program through the sites where they are employed. MI training will be conducted at sites as part of ongoing professional development.

Participation in the study includes:

PROTOCOL TITLE: TMI

(1) Fidelity Assessments: Quarterly for three years, participants will complete audio recorded standardized patient interactions (a total of 13) over the phone (approximately 30 minutes each) with a study staff member. The study staff member will role play as a patient with HIV and record the session, which will be rated using the MI Coach Rating Scale. This is being done to conduct assessments of their MI skills.

(2) MI training. An MI training workshop will be conducted as part of professional development at the sites. The timing of the training will depend on randomization (two sites are randomized to receive MI training every three months for up to 15 months). Prior to a participant's site's MI training, they will complete standard patient interactions quarterly. While the total number of interactions does not change, the number of interactions they do prior to training depends on their sites randomization and will vary from 2 to a maximum of 6. In the period following initial training, but before the next fidelity assessment, participants will complete two 1-hour coaching sessions over the phone. Following this period, participants may receive additional coaching quarterly for one year following the fidelity assessments described above.

After one year, sites will be randomized to internal facilitation (a person from each site will be chosen to be an MI supervisor to be available for ongoing fidelity monitoring and coaching) plus CoP (the site will decide how to meet as a group to continue MI practice), or to CoP only.

Implementation Teams (iTeams): There will also be an opportunity for some participants to be part of the iTeam at each site. The iTeam will meet monthly to review study progress and make recommendations for how best to implement and sustain MI at each Tailored Motivational Interviewing (TMI) Implementation Intervention site.

Data is formative, longitudinal, qualitative, and quantitative in nature.

7.0 Data and Specimen Banking*

The database will be password protected and stored on a password protected computer and cloud server.

At the end of the study data collected will be made available, in accordance with the NIH Data Sharing Policy (http://grants.nih.gov/grants/policy/data_sharing). These data will be saved for future use and may be shared with other researchers. The data stored and shared cannot be linked to participants (i.e., deidentified data will not link information to PHI, site, date, and city).

